3.2 Analysis time points

The timeframe encompasses the entire study duration, which extends from Screening to 10 weeks after the final dose, ie, 48 weeks of the Double-Blind Treatment Period and 6 weeks of the SFU Period.

The following study periods will be included in the analysis (see Section 3.3 for the definition of Relative day):

- Screening Period: up to 14 days (Day -14 through Day -1).
- Double-Blind Treatment Period: 48 weeks, starts with the randomization (1:2) of eligible participants to 1 of 2 treatment arms (SOC + placebo [PBO] or SOC + DZP 24mg/kg), stratified in accordance with the 3 stratification factors (see Section 4.1). Study medication will be administered by iv infusion every 4 weeks, starting on Day 1.
- Safety Follow-up Period (SFU):
 - Participants who withdraw from the study prematurely will be followed up for at least 10 weeks after the last infusion.
 - Participants who complete the 48-week Double-Blind Treatment Period, but do not enter the OLE study will continue into a 6-week SFU Period (10 weeks after last infusion at Week 44). During this period, study participants will not receive study medication, but will be able to receive SOC treatment, as indicated.

The time points for individual assessments are provided in the schedule of activities in Section 1.3, Table 1-2 in the SL0043 protocol.

Analyses conducted by visit will include each planned study visit at which the assessment was scheduled. Data for planned study visits will be based on the nominal time point and will not include any unplanned visits. Usually, efficacy data will not be obtained at unscheduled visits, with the exception of lab data used in the BILAG grading process and for SLEDAI-2K. Here, labs that are obtained prior to the visit or up to 2 weeks after the original visit could be used to replace missing lab data (see separate Central BILAG Grading and Adjudication Plan for details on the BILAG grading process).

All data collected, including assessments (planned or unplanned) will be reported in participant data listings. Data from participants withdrawing from the study early at end of treatment (EOT) visits will be mapped to the next scheduled visit per assessment for purpose of analyses and inclusion in summary tables but will be presented in terms of nominal visit in listings.

3.3 Relative day

Relative days for an event or measurement occurring before a reference date (generally the date of the first dose of study drug) are calculated as follows:

- Relative Day = (Event Date-Reference Date)

Relative days for an event or measurement occurring on or after the reference date to the last day of dose administration are calculated as follows:

- Relative Day = (Event Date-Reference Date) + 1

For events or measurements occurring after the date of last dose of study drug the relative day will be calculated with the date of last dose administration as reference. Relative day in this case will be prefixed with '+' in the data listings and will be calculated as follows:

- Relative Day = + (Event Date-Reference Date)

Note: relative day will be computed for fully reported dates only (for imputed dates it will not be computed)

3.4 Definition of Baseline values

Unless otherwise specified, the last value collected prior to the first infusion of study medication (Visit 2) will be used as the Baseline value. If a Baseline measurement is missing, and a Screening value is available, then the available Screening value will be utilized as Baseline. If a Baseline measurement is missing and there are multiple Screening lab values, then the most recent lab value prior to Baseline will be considered as the Baseline value. Unscheduled lab measurements taken before Baseline will be labelled as Screen Re-test values.

- For vital signs, a measurement prior to, or at the moment of, the start of the first infusion will be available for each visit. The last measurement prior to, or at the moment of, the start of the first infusion of study medication will be used as the Baseline value. An additional analysis will be performed using the pre-infusion values as Baseline values to determine the changes from pre infusion to post-infusion for each infusion visit. At each post-Baseline visit, the pre-infusion value will be one taken prior to, or at the moment of, the start of the infusion of study medication.
- For BILAG 2004 assessments, if the assessment is completed at Baseline, but the Grade for 1 or more individual system(s) is missing, the Grade for the system will be imputed as the Grade observed at the Screening visit. If there is no Grade available for the individual system at the Screening visit, then the Grade for that system at Baseline will be set to a Grade of BILAG 2004 D or E (in case no organ involvement ever before is documented).
- For SLEDAI-2K assessments, if a lab component for SLEDAI is missing at Baseline, the following methods will be applied.
 - If the last observation is present the last observation will be carried forward.
 - If there is no last observation the next observation will be carried backwards when there is one within the next 2 weeks.
 - If there are no observations under above two conditions the Baseline value will be set to ‘not present’.
 - Missing lab values that determine hematuria, pyuria or proteinuria at Baseline and at Screening will be imputed to 0.

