6.6.2 Escape medication

Although the use of escape medications is allowed at any time of the study, it should be delayed, if possible, for at least 8 weeks following the first administration of study treatment. Data from Phase 1 and Phase 2 studies suggest that DZP has a fast onset of action however it can take several weeks until the potential therapeutic effect of DZP fully develops. Escape treatment should be initiated as clinically indicated by the Investigator or other qualified physicians

treating the participant. Investigators should discuss the impact of escape treatment use on study conduct with the Medical Monitor before initiation.

Initiation of escape treatment may be handled as intercurrent event in estimands, which will be detailed in the statistical analysis plan (SAP) as described in Section 9.3.1. For the primary endpoint, specification of how escape treatment will be handled as an intercurrent event is detailed in Section 8.1.3.1, Section 9.3.1, and Section 9.6.

The date and time of escape medication administration as well as the name and dosage regimen of the escape medication must be recorded.

In case of use of escape treatment the study medication does not have to be automatically discontinued, however if the escape treatment in combination with DZP represents a safety concern (see Section 6.6) for the study participant the study medication should be discontinued but the study participant should remain in the study under observation. Investigators are advised to contact the Medical Monitor upfront if possible, to discuss the potential impact on the further study conduct in case study medications should be permanently discontinued.

The following escape medications may be used as indicated:

- Corticosteroids (new initiation or increase in dose)
- Immunosuppressants (new initiation or increase in dose):
 - azathioprine
 - methotrexate
 - mycophenolate mofetil
 - tacrolimus
 - low dose cyclophosphamide
 - cyclosporine
 - voclosporin

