9.2.3 Definition of Baseline values

Unless otherwise specified, the last value obtained prior to the first infusion of study medication (Visit 2) will be used as the Baseline value. If a Baseline measurement is missing, and a Screening value available, the Screening value will be utilized as Baseline instead.

For vital signs, a measurement prior to, or at the moment of, the start of the first infusion will be available for each visit. The last measurement prior to, or at the moment of, the start of the first infusion of study medication will be used as the baseline value. An additional analysis will be performed using the pre-infusion values as baseline values and determine the changes from pre-infusion to post-infusion for each infusion visit. At each post-Baseline Visit, the pre-infusion value will be one taken prior to, or at the moment of, the start of the infusion of study medication.

For Baseline assessments, if the BILAG 2004 is completed, but the grade for 1 or more individual system(s) is missing, the grade for the system will be set to a grade of BILAG 2004 D if no value can be imputed from the Screening Visit. This is a conservative approach for study participants on active doses, since no improvement can occur following a baseline grade of BILAG 2004 D level disease.

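### SAP 3.4 lets a missing Baseline SLEDAI-2K laboratory item be filled from a sample that will ordinarily be drawn after the first infusion

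*SAP*

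**What the plan says.** Both documents give the same general rule, each opening with a proviso for cases specified otherwise. In protocol 9.2.3, "the last value obtained prior to the first infusion of study medication (Visit 2) will be used as the Baseline value". In SAP 3.4, "the last value collected prior to the first infusion of study medication (Visit 2) will be used as the Baseline value".

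SAP 3.4 then sets out a sequence for a SLEDAI-2K laboratory component that is missing at Baseline:

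1. "If the last observation is present the last observation will be carried forward".
2. "If there is no last observation the next observation will be carried backwards when there is one within the next 2 weeks".
3. "If there are no observations under above two conditions the Baseline value will be set to" not present.

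A last bullet covers three urinary items: "Missing lab values that determine hematuria, pyuria or proteinuria at Baseline and at Screening will be imputed to 0".

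On timing, SAP 3.2 states: "Study medication will be administered by iv infusion every 4 weeks, starting on Day 1". Protocol 6.3 places randomization at the Baseline Visit, also Day 1.

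Two other rules bear on the point. Protocol 9.2.2 and SAP 3.2 allow laboratory results from up to 2 weeks after a visit to replace missing ones for BILAG and SLEDAI-2K, and neither excepts Baseline. Protocol 9.6, on a missing BILAG laboratory result at Baseline, looks only at Screening, Baseline and unscheduled predose results; failing those, the organ system is graded D.

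**The concern.** A Baseline value should not be open to influence by the assigned treatment. Randomization makes predose values comparable between arms in expectation; it gives no such assurance for a value measured after the first dose. Step 2 lets such a value in for one instrument, without a stated reason, while the companion rule for BILAG keeps it out.

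Baseline SLEDAI-2K is used in inferential endpoints. Protocol 8.1.3.1 makes no increase in SLEDAI-2K from Baseline a condition of BICLA response, so one laboratory item can decide a participant's status. BICLA is the primary endpoint at Week 48 and a key secondary at Weeks 24 and 12. Change from Baseline in SLEDAI-2K at Week 48 is a further key secondary.

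**Working it through.** **Can the window reach a post-dose sample?** The Baseline Visit and first infusion are both Day 1. Two weeks later is Day 1 + 14 = Day 15. A sample drawn after the Baseline Visit and by Day 15 is post-dose unless the first infusion was itself delayed to a separate day. The step does not ask which.

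**How often can step 2 be reached?** All of the following must hold.

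- The item is missing at Baseline and there is no earlier observation. Protocol 8.1.1.2 has the Screening SLEDAI-2K include laboratory items, protocol 5.1 requires that score to be at least 6, and protocol 6.3 stratifies on it. An earlier value should nearly always exist.
- A sample falls inside the window. In the Schedule of Activities the next visit is Day 28 ± 3 days, so Day 25 at the earliest, which is after Day 15. Only an unscheduled or repeat sample qualifies.
- The item is not taken by the urinary rule. SAP 6.2 lists eight laboratory-dependent descriptors. Three (hematuria, pyuria, proteinuria) have the zero rule, although its precedence over step 2 is not stated. That leaves 8 − 3 = 5 clearly exposed: urinary casts, low complement, increased DNA binding, thrombocytopenia and leucopenia.

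**What does each rule do to Baseline?** Take one item with score weight w. Let T be its true predose status and P its post-dose status (1 present, 0 absent).

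| Rule | Item score used | Error against the true value | Expected score, DZP minus placebo |
|---|---|---|---|
| Carry backward | w × P | w × (P − T) | w × [Pr(P=1, DZP) − Pr(P=1, placebo)] |
| Not present | 0 | −w × T | 0 |

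Among participants who reach the step, the not-present rule can understate Baseline, but the score it assigns does not depend on treatment. Carrying backward is free of treatment influence only if treatment leaves the item unchanged within two weeks. Relative to not present, it can only keep or raise Baseline (w × P ≥ 0), which makes the no-increase condition easier to meet. If DZP clears the item early, that help goes more often to placebo; if DZP makes the item more frequent, it goes more often to DZP. The documents settle neither.

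**Size per participant.** Planned arms are 208 (DZP) and 104 (placebo), with a planned difference of 0.52 − 0.32 = 0.20 (protocol 9.8, SAP 2.4).

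- One DZP participant reclassified: 1/208 = 0.0048, and 0.0048/0.20 = 2.4% of the planned difference.
- One placebo participant reclassified: 1/104 = 0.0096, and 0.0096/0.20 = 4.8%.

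**Power, for scale.** The plan states 90% (Fisher's exact, 2-sided 0.05). Full enumeration of both binomials gives 0.911, so the figure is reproduced. The documents give no rate of missing laboratory items, so the share f below is an assumption. It is an extreme bound in one direction: every affected DZP responder is lost, so the DZP rate is 0.52 × (1 − f), with placebo unchanged.

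| f (assumed) | DZP participants, 208 × f | DZP rate | Power |
|---|---|---|---|
| 0 | 0 | 0.5200 | 0.911 |
| 0.5% | 1.04 | 0.5174 | 0.904 |
| 1% | 2.08 | 0.5148 | 0.896 |
| 2% | 4.16 | 0.5096 | 0.879 |
| 5% | 10.4 | 0.4940 | 0.819 |

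The fix would not recover this power, because not present never gives a higher Baseline than carrying backward. The case for the fix is independence from treatment.

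**The case against.** The strongest reply is that step 2 is deliberate and consistent with the rest of the plan. Both general rules allow exceptions, step 2 is an express exception within the same section, and its 2-week window matches protocol 9.2.2 and SAP 3.2. A reader might infer that the SAP contradicts the protocol; the documents do not support that. What remains is an exception with no stated reason and no predose limit.

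A reader might also rely on protocol 6.6.2, "Data from Phase 1 and Phase 2 studies suggest that DZP has a fast onset of action", to argue that two weeks is long enough to bias Baseline by arm. The same sentence goes on to say that the full effect can take several weeks, and protocol Appendix 12 describes fast onset as response within 12 to 24 weeks. Neither place shows laboratory items changing within two weeks of one infusion. Differential bias is possible but not shown.

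Not present has its own cost. It replaces a measured result with the lowest score in a population that needs serological evidence at Screening, and a later positive item would then count as an increase. This stands as a trade-off: some misclassification, the same for either treatment, in exchange for a Baseline free of post-dose data.

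Finally, SAP 4.3.1, the efficacy section and the appendices are redacted in the public copy, and a predose limit there cannot be excluded.

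**Conclusion.** The concern holds as a narrow point of wording. As visible, SAP 3.4 permits a post-dose result to define a Baseline SLEDAI-2K laboratory item, and the 2-week window in protocol 9.2.2 and SAP 3.2 does not prevent it. The affected set should be very small, each reclassified participant is worth about 0.005 (DZP) or 0.010 (placebo) in responder rate, and the direction is unknown. It would be tempting to conclude that the primary result is biased in favor of DZP; nothing in the documents supports that, and if the drug clears an item early, carrying backward would, relative to not present, help placebo more often.

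This rests on the first infusion being given at the Baseline Visit as scheduled, on Screening laboratory results being obtained as the protocol requires, and on no further limit in the redacted text. The point is minor, and is worth making because the remedy costs almost nothing.

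**What to change.** - In SAP 3.4, limit the carry-backward step to samples drawn before the first infusion. If there is none, go to the existing not-present step. The limited step would still serve a participant whose first infusion is delayed beyond the Baseline Visit.
- In SAP 3.2 and protocol 9.2.2, except Baseline from the 2-week replacement window. Editing SAP 3.4 alone would leave a second route to the same post-dose replacement. The exception also brings these sections into line with the predose BILAG rule in protocol 9.6. If no further protocol amendment is planned, the change can be recorded in SAP Table 3-1.
- Report, by arm, how many participants have a Baseline SLEDAI-2K item filled by each step.

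The cost is a few lines of text and one small table, with no new data and no change to sample size or planned power. The downside is that a few participants would have an item scored as not present instead of by a measured post-dose result. That may understate their Baseline, but independently of treatment. The change should be made before unblinding.

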3.5 Protocol deviations

Important protocol deviations (IPDs) are a subset of protocol deviations that may significantly impact the completeness, accuracy, and/or reliability of the study data or that may significantly affect a participant's rights, safety, or well-being.

The criteria for identifying IPDs will be defined within the Protocol Deviation Specification Form. IPDs will be reviewed as part of the ongoing data cleaning process and data evaluation. All IPDs will be identified and documented prior to unblinding to confirm exclusion from analysis sets.

Sources for identifying protocol deviations will include the clinical database and a cumulative protocol deviation log from the clinical sites. Protocol deviations will be classified at blinded

data cleaning and data evaluation meetings. Any exclusion of participants from analysis sets or individual data from summary outputs will be documented in the meeting minutes.

For participants enrolled under different versions of the protocol, the programming of protocol deviations should be performed according to the version of the Protocol Deviation Specification Form relevant to the specific protocol version. The Protocol Deviation Specification Form will provide further details with regards to which version of the protocol the specific Protocol Deviation Specification Form version is applicable to. The version of the protocol to be followed for each participant will be provided by the Project Manager.

3.6 Analysis sets

The population of interest defined in Section 1, will be managed for statistical/reporting purposes using the following analysis datasets:

3.6.1 Enrolled Set

The Enrolled Set (ES) will consist of all study participants who have given informed consent.

3.6.2 Randomized Set

The Randomized Set (RS) will consist of all randomized study participants.

3.6.4 Safety Set

The Safety Set (SS) will consist of all study participants who are randomized and have received at least 1 dose (any amount) of study medication. Safety endpoints will be analyzed using the SS. In the case of any mistreated participants, participants will be analyzed 'as randomized' unless there is evidence the participant consistently received incorrect treatment, in which case an 'as treated' approach will be followed (which will consider the actual treatment received).

Note that site 50273 is included in the SS.

3.6.5 Per-Protocol Set

The Per-Protocol Set (PPS) will consist of study participants in the FAS who have received at least 1 full dose of study medication and have no important protocol deviations during the Treatment Period that may influence the validity of the data for the primary efficacy variable.

3.6.6 The Pharmacokinetic Per-Protocol Set

The Pharmacokinetic Per-Protocol Set (PK-PPS) consists of all study participants who received at least 1 dose of study medication and provided at least one quantifiable plasma concentration post-dose without important protocol deviations that would affect the concentration. Note that site 50273 is included in the PK-PPS.

3.7 Treatment assignment and treatment groups

For all analyses (where applicable) the results will be presented by treatment group:

- SOC + PBO iv q4w
- SOC + DZP 24mg/kg iv q4w

Selected parameters (where stated in the following sections) may be summarized also by subgroup (definition of subgroups, Section 4.9.1). A column for ‘All Participants’ will be added to group all participants regardless of treatment group, in the disposition, demographics, Baseline characteristics, prior and concomitant medications, corticosteroid dose at Screening and Baseline, exposure and Adverse Events (AEs) summary tables.

3.8 Center pooling strategy

There is no pooling strategy (by sites) defined for this study. Results will be combined across all sites, or by region according to the specified analysis.

3.9 Coding dictionaries

All AEs, concomitant diseases, and medical history will be coded for analysis according to the Medical Dictionary for Regulatory Activities (MedDRA)® coding dictionary, version 24.0. Prior and concomitant medications will be coded for analysis using the World Health Organization Drug dictionary (WHO-DD), Sep/2020 B3. The version number of coding dictionary will be displayed within the table. The coding dictionaries used to code adverse events (AEs), medical history, concomitant medications and concomitant diseases will be specified.

3.10 Changes to protocol-defined analyses

Table 3-1: Changes to the protocol defined analyses

Current in the protocol	Change
Tertiary endpoints: Observed values and change from Baseline in [REDACTED] [REDACTED] [REDACTED] [REDACTED] [REDACTED] levels in all	Observed values and change from Baseline in [REDACTED] [REDACTED] [REDACTED] [REDACTED] [REDACTED] [REDACTED] levels in all study

Table 3-1: Changes to the protocol defined analyses

study participants by visit and in study participants ‘positive’ at Baseline by visit	participants by visit and in study participants ‘positive’ at Baseline by visit.
Tertiary endpoints: Achievement of a meaningful improvement in CLASI Index by visit for all study participants and for subset of study participants with high CLASI	Achievement of a meaningful improvement in CLASI activity score by visit for all study participants, for subset of study participants with high CLASI, and study participants with a CLASI ≥ 10
Tertiary endpoints: Observed values and change from Baseline in [REDACTED] [REDACTED] [REDACTED] [REDACTED] [REDACTED] [REDACTED] levels in all study participants by visit and in study participants ‘positive’ at Baseline by visit	Added [REDACTED] conversion to the immunological parameters of DZP that will be evaluated
Tertiary endpoints: Achievement of reduction in corticosteroid dose from ≥ 7.5 mg/day prednisone equivalent dose at start of study to ≤ 5 mg/day prednisone equivalent at Week 24 and maintaining low corticosteroid dose and achievement of BICLA response at Week 48	Achievement of reduction in corticosteroid dose from >5mg/day prednisone equivalent dose at start of study to ≤ 5 mg/day prednisone equivalent at Week 24 and maintaining low corticosteroid dose and achievement of BICLA response at Week 48
Tertiary endpoints: Achievement of reduction of corticosteroid dose from >7.5 mg/day prednisone equivalent dose at start of study to ≤ 7.5 mg/day prednisone equivalent at Week 24 and maintaining low corticosteroid dose and achievement of prevention of moderate/severe BILAG flares (moderate/severe BILAG flare-free) at Week 48	Achievement of reduction of corticosteroid dose from >7.5 mg/day prednisone equivalent dose at start of study to ≤ 7.5 mg/day prednisone equivalent at Week 24 and maintaining low corticosteroid dose and achievement of prevention of moderate/severe BILAG flares (moderate/severe BILAG flare-free) through Week 48
Tertiary endpoints: Achievement of reduction in corticosteroid dose from >5 mg/day prednisone equivalent dose at start of study to ≤ 5 mg/day prednisone	Achievement of reduction in corticosteroid dose from >5 mg/day prednisone equivalent dose at start of study to ≤ 5 mg/day prednisone equivalent at Week 24 and maintaining low

Table 3-1: Changes to the protocol defined analyses

equivalent at Week 24 and maintaining low corticosteroid dose and achievement of BICLA response at Week 48	corticosteroid dose and achievement of BICLA response at Week 48
Tertiary endpoints: Achievement of reduction of corticosteroid dose from ≥ 7.5 mg/day prednisone equivalent dose to ≤ 5 mg/day prednisone equivalent at Week 24 and maintaining low corticosteroid dose and achievement of prevention of moderate/severe BILAG flares (moderate/severe BILAG flare-free) at Week 48	Achievement of reduction of corticosteroid dose from >5 mg/day prednisone equivalent dose to ≤ 5 mg/day prednisone equivalent at Week 24 and maintaining low corticosteroid dose and achievement of prevention of moderate/severe BILAG flares (moderate/severe BILAG flare-free) through Week 48
To the current tertiary endpoints:	
Added:
 
• Achievement of a meaningful improvement in CLASI activity sub score – erythema by visit for all study participants and for subset of study participants with high CLASI• Achievement of a meaningful improvement in CLASI activity sub score – scaling by visit for all study participants and for subset of study participants with high CLASI• Achievement of a meaningful improvement in CLASI activity sub score – alopecia by visit for all study participants and for subset of study participants with high CLASI• Change from Baseline in Clinical SLEDAI-2K by visit 
Revised definition of DORIS:
 
- Clinical SLEDAI-2K score =0 (SLEDAI-2K without serology: [REDACTED] [REDACTED] - PGA ≤ 16mm- Prednisone equivalent systemic dose for a SLE indication ≤ 5mg per day at $>50\%$ of the last 28 days (>14 of the last 28 days) and the prednisone dose is

[figure not shown]
Table 3-1: Changes to the protocol defined analyses

[figure not shown]
	
$\leq 5\text{mg/day}$ at all days in the 7 days before a visit, at the day of the visit and at the day after the visit
 
- [REDACTED] $\leq \text{ULN}$
 
- [REDACTED] $\geq \text{LLN}$

To the current primary efficacy subgroup analyses:	[REDACTED]

